5.4 Method for Assigning Subjects to Treatment Groups

Randomization of 1:1 will be assigned at the time of accrual. At the outpatient offices of the Department of Otolaryngology- Head and Neck Surgery, subjects will be randomly assigned to receive either a metformin or placebo. The Division of Biostatistics will generate the randomization schedule prior to the initiation of the study using the method of random permuted blocks. Randomization assignments will be loaded into a REDCap

database, and assignments will be accessed by the study coordinator using the REDCap randomization facility.

5.5 Preparation and Administration of Study Drug/Therapy

Metformin tablets will be provided by the Department of Otorhinolaryngology and will be coordinated through the Thomas Jefferson University Hospital Investigational Drug Service (IDS) Pharmacy. Drug will be stored in locked cabinet until given to the participants. A three week supply of metformin and placebo will be provided to subjects and the drug will be self-administered by the participants.

5.6 Subject Compliance Monitoring

There will be a pill bottle with the appropriate number of metformin or placebo tablets distributed to the patients upon enrollment into the trial. The pill bottle will be accompanied with detailed instructions on the proper dosage/number of tablets to take daily as noted above. At the first visit following completion of metformin administration (approximately 2 weeks after RAI), the bottle will be collected by the trial coordinator and the contents will be evaluated for compliance.

5.7 Prior and Concomitant Therapy

All medications are permitted except those that are contraindicated with metformin under current FDA recommendations. It is important to note that the medications that are contraindicated with metformin are contraindicated due to concern for theoretical interactions.

5.8 Packaging

Metformin will be provided by the Department of Otorhinolaryngology and will be coordinated through the Thomas Jefferson University Hospital Investigational Drug Service (IDS) Pharmacy. The study drug will be packaged in 1 bottle containing 500mg tablets for a maximum of 3 weeks. The bottle will be labeled "take one tablet daily for three days then one tablet twice daily for three days then two tablets twice daily until the day before the RAI treatment. Resume two tablets twice daily the day after RAI treatment until the end of the bottle".

5.9 Blinding of Study Drug

The bottle will be non-descript and contain either metformin or placebo depending on randomization. Patient will be blinded to which pill (metformin or placebo) they will receive. Pill bottle distribution will be completed by the research coordinator who will not be blinded. Principal investigator and care providers making assessments will not be blinded.

5.10 Receiving, Storage, Dispensing and Return

5.10.1 Receipt of Drug Supplies The study drug will be provided by the Department of Otorhinolaryngology and will be coordinated through the Thomas Jefferson University Hospital Investigational Drug Service (IDS) Pharmacy. Upon receipt of the study treatment supplies, an inventory must be performed and a drug receipt log will be filled out and signed by the person accepting the shipment. It is important that the designated study staff counts and verifies that the shipment contains all the items noted in the shipment inventory. Any damaged or unusable study drug in a given shipment (active drug or comparator) will be documented in the study files. The investigator must notify study sponsor of any damaged or unusable study treatments that were supplied to the investigator's site.

Upon completion or termination of the study, all unused and/or partially used investigational product will be destroyed at the site per institutional policy. It is the Investigator's responsibility to arrange for disposal of all empty containers, provided that procedures for proper disposal have been established according to applicable federal, state, local and institutional guidelines and procedures, and provided that appropriate records of disposal are kept.

5.10.2 Storage Drug will be stored in a locked cabinet until given to the participants at room temperature in the Thomas Jefferson University Hospital Investigational Drug Service (IDS) Pharmacy. The investigator must ensure that it is stored in accordance with the environmental conditions as defined in the package insert. Clinical supplies may not be used for any purpose other than that stated in the protocol.

5.10.3 Dispensing of Study Drug The study drug will be dispensed to the participants in 1 bottle containing approximately 69 500mg tablets for a maximum of 3 weeks. The bottle will be labeled "The bottle will be labeled "take one tablet daily for three days then one tablet twice daily for three days then two tablets twice daily until the day before the RAI treatment. Resume two tablets twice daily the day after RAI treatment completion until the end of the bottle." The amount of pills dispensed to every participant will be logged in the accountability logs by the pharmacist. The participant will be instructed to bring the bottle and all the pills that were not taken the day of his surgery. Regular study drug reconciliation will be performed only at the end of the study.

5.10.4 Return or Destruction of Study Drug

Regular study drug reconciliation will be performed at the end of the study. Drug that was assigned, drug consumed, and drug remaining will be logged in the drug accountability form and will be signed and dated.

At the completion of the study, there will be a final reconciliation of drug purchased, drug consumed, and drug remaining. This reconciliation will be logged on the drug reconciliation form, signed and dated. Any discrepancies noted will be investigated,

resolved, and documented prior to destruction of unused study drug. Drug destroyed on site will be documented in the study files.

5.11 Placebo

Placebo will be given as 500mg capsules twice daily. Placebo will be in capsule form. It will be stored in a locked cabinet until given to the participants at room temperature in the Thomas Jefferson University Hospital Investigational Drug Service (IDS) Pharmacy.

The placebo will be packaged in bottles containing approximately forty-two (42) 500mg capsules. The bottle will be labeled "take one capsule twice daily until the day before the RAI treatment. The day after RIA treatment completion, resume one capsule twice daily until the end of bottle.".

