3.0 STUDY DESIGN

3.1 General Design

Type of trial: Pilot Efficacy trial

Planned accrual period: 48 months

Planned follow-up period: 12 months

Planned enrollment: Total of 32 patients

Schema of the trial design, procedures, and stages:

Patients with a diagnosis of well-differentiated thyroid cancer who have undergone tumor resection and have indications for RAI treatment that meet our inclusion and exclusion criteria will be offered participation in this clinical trial. Patients who present to TJUH with a known diagnosis of differentiated thyroid cancer who plan to undergo surgical resection followed by radioactive iodine will be offered enrollment in the trial at the time of surgical scheduling. Patients who undergo lobectomy for atypia of undetermined significance/follicular lesion of undetermined significance or follicular neoplasm/suspicious for follicular neoplasm who are subsequently found to a malignancy will be offered enrollment at their first follow-up visit. After informed consent is signed and study subjects are randomized 1:1 to take metformin or placebo, patients will be administered metformin with dose escalation as tolerated until time of RAI treatment. There is no dose escalation for patients randomized to the placebo arm. Pre-operative and pre-RAI treatment CBC with differential will be compared to post-RAI treatment lab values. Standardized surveys assessing symptoms of xerostomia, sialadenitis, xerophthalmia and dysgeusia will be completed.

Participants' Follow-up: Participants' will have blood and saliva samples drawn post-op before metformin administration, before and immediately following RAI treatment, after metformin, and then every three months for 12 months. They will complete surveys at each post-op visit, and their medical records will be reviewed every 3 months for 12 months to assess for symptoms of myelosuppression, xerostomia, xerophthalmia, and dysgeusia. This will allow us to assess the radioprotective effects of metformin post-RAI treatment.

Purpose of the study: To estimate the radioprotective effect of metformin in subjects with differentiated thyroid cancer by evaluating both the ability of metformin to mitigate known side effects of radioactive iodine therapy as well as alter the exosome profile in the serum.

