8.2 Recording of Adverse Events

At each contact with the subject, the investigator will seek information on adverse events by specific questioning and, as appropriate, by examination. Information on all adverse events will be recorded immediately in the source document, and also in the appropriate adverse event module of the case report form (CRF). All clearly related signs, symptoms, and abnormal diagnostic procedures results should be recorded in the source document, though should be grouped under one diagnosis.

All adverse events occurring during the study period will be recorded.

The clinical course of each event will be followed until resolution, stabilization, or until it has been determined that the study treatment or participation is not the cause. Serious adverse events that are still ongoing at the end of the study period will be followed up to determine the final outcome. Any serious adverse event that occurs after the study period and is considered to be possibly related to the study treatment or study participation will be recorded and reported immediately.

8.3 Unblinding Procedures:

At the completion of the accrual period subjects will remain blinded until after the primary and secondary endpoints have been collected. Once study is complete, PI will unblind patients to their randomization upon request.

8.4 Stopping Rules:

Grade 4 toxicity (probably or definitely drug related): Treatment will be discontinued definitively.

Participants will be discontinued from study drug as per physician discretion

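### The stated patient blind is not secured, because the two arms' bottles differ in label text, unit count and possibly dosage form

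*Combined protocol and SAP*

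**What the plan says.** Section 5.9 sets out the blind: "The bottle will be non-descript and contain either metformin or placebo depending on randomization", and "Patient will be blinded to which pill (metformin or placebo) they will receive". The same section says that the coordinator, the principal investigator and the assessing care providers are not blinded, so the patient blind is the only one the protocol claims. Section 8.3 says how long it lasts: "At the completion of the accrual period subjects will remain blinded until after the primary and secondary endpoints have been collected".

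The products are described elsewhere:

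- **Metformin (Section 5.10.3).** Supplied "in 1 bottle containing approximately 69 500mg tablets for a maximum of 3 weeks", with a label that begins "take one tablet daily for three days then one tablet twice daily for three days then two tablets twice daily". Section 5.8 gives the same steps.
- **Placebo (Section 5.11).** "The placebo will be packaged in bottles containing approximately forty-two (42) 500mg capsules". The label reads "take one capsule twice daily until the day before the RAI treatment", and one capsule twice daily resumes the day after RAI.
- **Escalation (Section 3.1).** "There is no dose escalation for patients randomized to the placebo arm". Appendix A, footnote H, agrees.
- **Dosage form.** Metformin is a tablet throughout. Placebo is a capsule in Section 5.11 but a tablet in Section 5.6 and in footnote H.

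Section 5.6 adds that written instructions on how many units to take each day come with the bottle. No section describes matched appearance, over-encapsulation, a dummy escalation or a label common to both arms.

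**The concern.** A plain bottle conceals the arm only if what is in it and what is printed on it are also uninformative. Here the label wording and the number of units depend on the arm, and the dosage form may as well. Under Section 6.1 the coordinator takes candidates through the protocol before consent. A patient who learns there that metformin is stepped up and placebo is not needs only their own label to work out the arm. The phone calls on escalation days (Sections 1.4 and 5.3) would be a further cue if they were made only in the metformin arm; the documents do not say.

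At stake are the outcomes that patients report themselves: the xerostomia, xerophthalmia and dysgeusia questionnaires in Section 2.2 and, to a degree, reported tolerability. The synopsis treats the secondary analyses as mainly descriptive, but Section 7.2 plans mixed models for the other longitudinal outcomes, so the arms will be compared. If some patients infer their arm, part of any symptom difference could be expectation, while the protocol text would support an unqualified claim that patients were blinded.

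**Working it through.** **Inputs.** The metformin label steps and count come from Section 5.10.3, and the placebo label and count from Section 5.11. Dosing starts one week before RAI (Sections 1.4 and 6.1) and runs for two weeks after it (Section 6.1), which gives 7 + 14 = 21 dosing days. The optional two-week delay window in Section 1.4 is assumed unused.

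**Step 1: reproduce the plan's counts.**

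- Metformin at full tolerated dose: 3 × 1 + 3 × 2 + (1 + 14) × 4 = 3 + 6 + 60 = 69 tablets.
- Placebo: 21 × 2 = 42 capsules.

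Both match the stated figures exactly. The difference is 69 − 42 = 27 units and the ratio is 69/42 = 1.64. The mismatch therefore comes from two different labelled regimens.

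**Step 2: compare the daily units.**

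| Dosing days | Metformin label | Placebo label | Differ? | Days |
|---|---|---|---|---|
| 1 to 3 | 1 | 2 | yes | 3 |
| 4 to 6 | 2 | 2 | no | 3 |
| 7 | 4 | 2 | yes | 1 |
| 14 days after RAI | 4 | 2 | yes | 14 |

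At full tolerated dose the daily number differs on 3 + 1 + 14 = 18 of 21 days (86%).

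**Step 3: vary the tolerance.** A metformin patient who stays at 500 mg twice daily after day 3 takes 3 × 1 + 18 × 2 = 39 units and differs from placebo on 3 of 21 days (14%). The label wording and the dispensed count still differ for this patient, because neither depends on tolerance.

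**Step 4: the schema wording.** The synopsis schema puts the top step from day 6, which conflicts with the three days at the middle step in the same sentence. Taking day 6 literally gives 3 × 1 + 2 × 2 + (2 + 14) × 4 = 71 tablets and a difference on 3 + 16 = 19 of 21 days (90%). Since 71 is not the dispensed 69, the Section 5.10.3 label is the better basis, and the conclusion does not rest on this reading.

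**Step 5: count the exposed assessments.** Questionnaires are completed at Visit 2 and every three months for a year: 1 + 12/3 = 5 rounds, all after the patient has used the labelled bottle.

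**The case against.** The strongest reply is that nothing here breaks the blind outright. No patient sees both bottles, and neither label names an arm. An instruction to take one capsule twice daily tells a patient nothing unless that patient knows what the other arm takes. The link depends on what is said at consent; that wording is not available for this review, and the remark in Section 6.1 about going over the protocol is general. This stands, and it is why the conclusion is that the blind is not secured rather than that it fails.

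The day counts can also be challenged, because they compare two bottles that no one patient compares. That is right: 18 of 21 and 3 of 21 describe the products and are not rates of unblinding.

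Finally, this is a pilot of 32 patients. Its blood count and exosome outcomes are laboratory measures, its symptom outcomes are secondary, and Section 5.9 openly says that staff are not blinded. This limits how far the problem reaches. It does not remove it: patients complete the symptom questionnaires themselves, mitigation of symptoms is a listed objective in Section 2.0, and a descriptive comparison by arm is as open to expectation as a modelled one.

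**Conclusion.** The concern holds. The products as described do not deliver the patient blind stated in Sections 5.9 and 8.3. It is certain from the text that the label wording differs between arms, that about 69 units are dispensed in one arm and about 42 in the other, and that the placebo's dosage form is contradictory. The daily number of units differs on 3 to 18 of 21 days, depending on tolerance, if the planned 7 + 14 days are kept and the delay window is not used.

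Whether patients would infer their arm depends on what they are told about the two regimens, so unblinding is possible but not shown. The size of any resulting bias cannot be derived from the documents. The exposure is mainly to five post-treatment rounds of self-reported symptoms. This should be corrected, but it does not undermine the laboratory comparisons.

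**What to change.** Reconcile Sections 5.9 and 8.3 with Sections 3.1, 5.6, 5.8, 5.10.3 and 5.11 and Appendix A, footnote H, so that what the patient receives and reads does not reveal the arm, and settle whether the placebo is a capsule or a tablet. How this is achieved is for the sponsor; no dose or schedule is proposed here.

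At one bottle per patient this concerns at most 32 bottles, through the pharmacy that already coordinates supply. If metformin is a tablet and placebo a capsule, new labels alone would not make them alike and the product itself would need attention. The documents give neither price nor feasibility.

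If the products cannot be aligned, amend Sections 5.9 and 8.3 to say that patients are not told their arm but that product and label differ. Report the symptom comparisons with the limitation that the patient blind may be incomplete and the results are open to expectation bias. That costs two text changes and one reporting sentence; the price is a weaker blinding claim.

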6.0 STUDY PROCEDURES

6.1 Study Visit Schedule Screening: Trial Coordinator will screen the office charts for possible inclusion in the trial. Labs for the screening part will be available from pre-admission testing that is standard of care for initial biopsy. Women of childbearing potential (WOCBP) should have a pregnancy test done as part of pre-admission testing prior to surgery (within 14 days of study enrollment). If a test was not done, it will be done at time of consent.

Visit 1: Subjects who meet inclusion criteria after reviewing the initial biopsy, laboratory data, and clinical chart will be approached the day of their follow up after initial biopsy. The study coordinator will meet with the prospective candidates and go over the protocol, answer questions and obtain informed consent. If the subject is agreeable to the study, a physical exam will be performed, subject will be randomized and metformin or placebo will be dispensed. Instructions on how to take study drug will be given and times for follow up phone calls for tolerability and safety will be arranged with participants. Participants will be instructed to call with any side effects or adverse events that occur in the interim of the follow up phone calls.

The exact date to start the metformin will be determined this visit based on the planned date of radioactive iodine (RAI) administration. One week prior to the radioactive iodine treatment, the first dose of metformin can start. Metformin or placebo will be stopped the day before RAI treatment is received.

Per standard of care, a pregnancy test will be done within 72 hours of starting radioactive iodine administration.

Quality of life measures will be assessed prior to start of metformin.

Quality of life measures will be administered on an IPad through a website (https://az1.qualtrics.com/jfe1/preview/SV_57qgtgkjaexOy9f). Participants will be

identified only by study ID number. Paper questionnaires will be provided if the forms cannot be completed electronically.

Metformin or placebo administration will resume the day after the last treatment with radioactive iodine and will be taken until the end of bottle (2 weeks after RAI treatment).

Visit 2: At the first visit following completion of metformin administration for two weeks after RAI, patients will be approached for bottle and pill reconciliation, review of compliance with appropriate lab draws, as well as follow up of side effects and adverse events.

Follow-up: A follow up phone call will be performed 2 weeks after the last dose of metformin for any other side effects or adverse events. Every 3 months during the first year post-treatment subjects will have their regularly scheduled appointments at which we will draw blood/saliva, administer quality of life surveys, and review medical records.

Quality of life measures will be administered on an IPad through a website (https://az1.qualtrics.com/jfe1/preview/SV_57qgtgkjaexOy9f). Participants will be identified only by study ID number. Paper questionnaires will be provided if the forms cannot be completed electronically.

6.2 Definition of Dose-Limiting Toxicities and early stopping rules:

Toxicity will be evaluated using the most recent version (version 4) of the NCI toxicity criteria, i.e. the NCI Common Terminology Criteria for Adverse Events (CTCAE) version 4.0. The CTCAE provides descriptive terminology and a grading scale for each adverse event listed. A copy of the CTCAE can be found at <http://ctep.cancer.gov>.

Grade 4 toxicity (probably or definitely drug related): Treatment will be permanently discontinued.

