Schema	
32 patients with thyroid cancer who undergo primary surgical resection and subsequently require RAI treatment.
 
Preoperative blood and saliva
 
Thyroidectomy
 
Recovery for approx 6-8 weeks
 
Postoperative Pretreatment Metformin Blood and Saliva
  <pre> graph TD A[Postoperative Pretreatment Metformin Blood and Saliva] --> B[Randomized Metformin treatment* (n=30) or placebo treatment (n=30) 1 wk] B --> C[Post-metformin or placebo Pre-RAI Tx blood and saliva] C --> D[RAI Tx] D --> E[Post RAI blood and saliva] E --> F[Metformin or placebo Treatment** 2 wks] F --> G[Post-RAI Tx blood sample q 3mo x 12 mos] </pre> 
*Metformin (500 mg/day for 3 days followed by 500 mg twice daily for 3 days followed by 1000 mg twice daily from day 6 until RAI tx)
 
**Metformin (1000 mg twice daily for two weeks following RAI tx)

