2.0 STUDY OBJECTIVES

1. To estimate the capacity of metformin to mitigate radioactive iodine therapy-induced myelosuppression as assessed by CBC
2. To assess the capacity of metformin to mitigate known side effects of radioactive iodine therapy including xerostomia, xerophthalmia, and dysgeusia as assessed by standardized questionnaire
3. To analyze changes in serum and salivary exosome profiles following a trial of metformin administration in patients receiving radioactive iodine treatment

2.1 Primary Objective:

We have chosen complete blood count (CBC) as our primary endpoint and serum and salivary exosome profiles as secondary endpoints. To evaluate if treatment with metformin inhibits RAI-induced myelosuppression and induces faster recovery of white blood cell count to baseline values, the blood counts will be compared in the pre- and post-treatment samples. Blood parameters will include hemoglobin, red blood-cell count, white blood-cell count, absolute neutrophil count, absolute lymphocyte count, and

Thomas
Jefferson
University

platelet count. Blood and salivary samples will be drawn before surgery, before and immediately after treatment with metformin and RAI, and every three months thereafter for one year.

All blood samples will be taken by a phlebotomist or trained personnel. A baseline blood sample, consisting of two tubes of 1 cc of whole blood each, will be drawn before thyroidectomy as part of standard procedure at patients' pre-operative testing appointment. Patients will recover for a period of 6-8 weeks and identical samples will be drawn within 72 hours of starting metformin. Then samples will be drawn within three days before and within three days after RAI treatment, at the conclusion of metformin treatment, and every three months thereafter for one year. Blood parameters will include hemoglobin, red blood-cell count (RBC), white blood-cell count (WBC), absolute neutrophil count (ANC), absolute lymphocyte count (ALC), and platelet count. Assays will also be conducted on samples to assess metformin-induced changes in serum and salivary cytokines and growth factors, erythrocyte sedimentation rate (ESR), exosome evaluation, and metabolomics profile. 5 cc samples of patient saliva will be collected in specimen cups.

2.2 Secondary Objective:

- Assess safety and tolerability of metformin treatment in subjects undergoing RAI treatment for differentiated thyroid cancer

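### Section 6.1 randomises and dispenses at the post-biopsy visit while the schema randomises after surgery and recovery, so patients who never reach RAI can be randomised

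*Combined protocol and SAP*

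**What the plan says.** Section 6.1 states that eligible subjects "will be approached the day of their follow up after initial biopsy". At that visit they consent and are examined, and then the "subject will be randomized and metformin or placebo will be dispensed". The drug start date is also set there, "based on the planned date of radioactive iodine (RAI) administration".

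Other sections fit early allocation. Section 3.1 says patients with a known diagnosis "will be offered enrollment in the trial at the time of surgical scheduling". Section 5.4 assigns treatment when the patient is accrued, and 5.6 hands over the bottle at enrolment.

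The schema in the Study Summary gives a different order: thyroidectomy, "Recovery for approx 6-8 weeks", a post-operative blood and saliva sample, and only then the randomised metformin or placebo box. It describes the sample as "32 patients with thyroid cancer who undergo primary surgical resection and subsequently require RAI treatment". Section 2.1 agrees on when drug starts: "Patients will recover for a period of 6-8 weeks and identical samples will be drawn within 72 hours of starting metformin".

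Eligibility points both ways. The opening of 3.1 refers to patients "who have undergone tumor resection and have indications for RAI treatment", and inclusion criterion 1 (4.1) requires completed thyroidectomy and I-131 candidacy. Criterion 4 also accepts planned thyroidectomy, and the Study Summary's main inclusion criterion is a scheduled resection to be followed by RAI. Appendix A gives Visit 1 no date.

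**The concern.** RAI after thyroidectomy is not automatic. The protocol's own background (1.2) describes guidelines that recommend it for high-risk and selected low-risk patients. A patient randomised before surgery may therefore turn out not to need it. No section requires RAI to be confirmed before allocation, and none says how to handle a randomised patient who never receives it.

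How such a patient counts depends on which population text applies. Section 7.3 keeps everyone randomised with any data, as randomised. The time points in 7.2 are named by resection, so a patient who had surgery but no RAI can still supply values, and these dilute the treatment contrast. If there are no later counts, or if the Study Summary rule requiring both pre- and post-treatment samples is applied, the patient is lost to the primary comparison and uses up the attrition allowance. For any one patient these are alternatives, not cumulative effects.

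There is a secondary risk. Section 5.9 blinds only the patient. An RAI decision taken after allocation could be taken with the arm known. The documents do not say who decides, so this is a possibility and not a demonstrated bias.

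**Working it through.** **When allocation happens**

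| Source | Timing |
|---|---|
| 6.1, Visit 1 | Follow-up after initial biopsy; randomise and dispense |
| 3.1, first route | Enrolment at surgical scheduling |
| 3.1, lobectomy route | Enrolment at the first follow-up visit after surgery |
| 5.4 and 5.6 | Allocation at accrual; bottle at enrolment |
| 4.1, criterion 1 | Thyroidectomy already done, I-131 candidate |
| 4.1, criterion 4 | Thyroidectomy done or planned |
| Schema | After thyroidectomy, 6-8 weeks of recovery and a post-operative sample |

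The conflict concerns patients who enter before surgery. Those entering after lobectomy or a completed thyroidectomy are affected less.

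**The plan's own figure.** Inputs from 7.1: 95% confidence interval, half-width 0.78 SD, 14 per group, 10% attrition, 16 per group randomised. In SD units,

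half-width = t(0.975, 2n − 2) × √(2/n).

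- n = 14: 0.777
- n = 13: 0.810
- n = 16: 0.722

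So 14 is the smallest n that meets 0.78. Then 14/0.9 = 15.6, rounded up to 16 per group and 32 in total. The stated figures reproduce.

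**Adding never-RAI patients.** Let q be the share of each arm that is randomised but never receives RAI. It is not in the documents and is assumed here. If only a fraction of the arm enters before surgery, q is that fraction multiplied by the never-RAI share among those patients.

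*Case A: no usable post-treatment data, on top of 10% attrition.* Evaluable per arm = 16 × 0.9 × (1 − q). Number to randomise per arm to keep 14 = 14/[0.9 × (1 − q)], rounded up.

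| q | Evaluable per arm | Half-width (SD) | Randomised total to keep 14 per arm |
|---|---|---|---|
| 0 | 14.4 | 0.765 | 32 |
| 5% | 13.68 | 0.787 | 34 (14/0.855 = 16.4, so 17 per arm) |
| 10% | 12.96 | 0.811 | 36 (14/0.81 = 17.3, so 18 per arm) |
| 20% | 11.52 | 0.866 | 40 (14/0.72 = 19.4, so 20 per arm) |

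The evaluable number falls below 14 once q exceeds 1 − 14/14.4 = 2.8%. If the 10% allowance is taken to cover never-RAI patients and nothing else is lost, the threshold is 1 − 14/16 = 12.5%.

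*Case B: all never-RAI patients stay in follow-up and show no drug effect.* As-randomised contrast = 0.78 × (1 − q):

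- q = 10%: 0.78 × 0.9 = 0.702 SD
- q = 20%: 0.78 × 0.8 = 0.624 SD

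**The case against.** Five points can be made against this.

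1. **Eligibility may already block it.** Section 6.1 applies to subjects who meet the inclusion criteria, and criterion 1 requires completed thyroidectomy. Read strictly, nobody can be randomised before surgery. That reading leaves criterion 4's allowance for planned surgery, the surgical-scheduling route in 3.1 and the Study Summary's scheduled-resection criterion without effect. It is one of two available readings, which is why the claim is that 6.1 can randomise such patients, not that it must.
2. **The schema box may mark the start of treatment and not the act of allocation.** This is possible, and it would soften the conflict. Section 6.1 would still allocate and dispense weeks before use, and nothing would defer randomisation until RAI is confirmed.
3. **Visit 1 may be tied to RAI.** Appendix A marks radiation and study drug under Visit 1, and 6.1 sets the start date from the planned RAI date. But Appendix A marks radiation under Visit 2 as well, so it dates neither visit, and a planned date is not a confirmed one.
4. **The size is assumed.** This stands. Patients entered with RAI in view may have a small q. The 2.8% threshold is less than half a patient per arm (0.028 × 16 = 0.45). At q = 5% the half-width rises only from 0.777 (n = 14) to 0.787. Section 7.1 does not say what its 10% covers.
5. **As-randomised analysis is a sound choice, and clearer wording alone would remove the contradiction.** Both are true. However, rewording that kept pre-surgery allocation would leave the avoidable dilution or loss in place.

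**Conclusion.** The concern holds. The protocol gives two incompatible points for randomisation, and the eligibility text does not choose between them. Followed as written, 6.1 allows patients enrolled before surgery to be randomised and given drug before anyone knows whether they will receive RAI.

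The statistical cost depends on a share the documents do not give. At a few per cent it is slight. At 10-20% it is either a half-width of 0.81-0.87 SD in place of 0.78, or a contrast diluted to 0.70-0.62 SD. The first assumes these losses come on top of the planned 10% attrition. The second assumes full follow-up and no drug effect in untreated patients. The margin is two patients per arm and must also cover ordinary dropout. The problem is worth correcting mainly because the timing of allocation is contradictory and can be settled before it costs any patients; confidence in its size is moderate.

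**What to change.** Keep consent and the pre-operative sample where they are. Move randomisation and dispensing to the post-operative visit, after RAI has been scheduled, eligibility has been re-checked and the pre-metformin sample already planned in 2.1 has been drawn. Count the 32 from that point. Bring 3.1, inclusion criteria 1 and 4, 5.4, 5.6, 6.1 and the definition of Visit 1 in Appendix A into line with the schema.

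The cost is protocol wording and one visit definition. The planned N of 32 does not change and no new sample is needed. The drawback is that some consented patients will not be randomised and must be replaced, so more than 32 may need to be consented.
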